
**SA1:** Examine the effect of the *BSM* intervention on the primary outcome of BNP intensity and interference between the intervention and attention control group controlling for prior BF experience across all data points.

**H1:** The *BSM* group will report significantly lower BNP intensity and interference at 1, 2, and 3 weeks and significantly lower cumulative BNP score over time compared to the AC group.

**SA2:** Examine the effect of the *BSM* intervention on secondary outcomes of BF exclusivity, BF self-efficacy, and maternal well-being.

**H2A:** The *BSM* group will have a higher proportion of women with exclusive BF at 6, 9, 12, 18, and 24 weeks and higher BF self-efficacy at all-time points compared to the attention control group. **H2B:** The *BSM* group will have higher maternal well-being compared to the attention control group at each time point.

**SA3:** Explore (1) the influence of pain sensitivity (quantitative sensory testing, select buccal cell and/or blood samples for pain sensitivity SNPs and in a subsample, DNA methylation of select sensitivity SNPs (40 participants (5 zero and 15 highest pain phenotype per group) on BNP intensity and interference; and (2) BF outcomes in SA2, maternal and pain self-efficacy over time between groups.

**SA4:** Explore (1) the influence of pain sensitivity and lactation (blood samples for pain sensitivity and lactation SNPs [*OXTR* and *PRL*]) on perception of milk supply (BSES and HH lactation scale).

Aligned with the Maternal and Infant Care goals of Healthy People 2020, NINR strategic themes of symptom science and self-management, NICHD optimal infant and maternal health during the fourth trimester, and the CDC *HEAR HER* campaign, the proposed study will address a major barrier to BF initiation and exclusivity by testing the effectiveness of the *BSM* intervention to decrease BNP intensity and interference and increase BF self-efficacy and support maternal well-being. The *BSM* intervention is easily accessible and clinically sustainable allowing for large-scale translation in health care and public health settings.

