**Justification of Sample Size:**

The sample size objective for the study is to recruit  $N = 280$  women who will be randomly assigned to the *BSM* or attention control study groups at a 1:1 ratio (140 per group). This objective provides 80% power ( $\alpha = 0.05$ , two-sided) to detect a standardized mean difference (Cohen's  $d$ ) of 0.39 or more between the *BSM* and attention control groups. It also provides 80% power to detect an odds ratio of 2.5 or more in exclusive BF between the two groups, assuming that the exclusive BF rate of the control group will be 10% higher than the national population rate in 2017 at 6, 9, 12, 18, and 24 weeks. These calculations account for "loss to follow-up" as high as 25% at 24 weeks, despite the substantially lower attrition (6%) in our pilot study. Based on our pilot study, we approached 78 women to meet our sample size of 60, with a failed screening rate of 25%. Thus, we intend to approach 374 women, which is 25% higher than our proposed study sample to meet our sample size. We anticipate that approximately 70% of the study sample will be WAHS or HHC patients.

In the pilot study, RM-ANCOVAs (with the baseline value of a measure as the covariate) revealed standardized mean differences larger than  $d = 0.39$  for the "main effect" of the intervention on BNP intensity ( $d = 0.45$ ), pain severity ( $d = 0.60$ ), cumulative pain ( $d = 0.64$ ), and BF self-efficacy ( $d = 0.48$ ) across the 1-, 2-, and 6-week time points. For BNP interference, the value of  $d$  was 0.39 at week 1, but smaller at weeks 2 and 6. Furthermore, the odds of exclusive BF in the intervention group are 2.9 times higher than the control group at 6 weeks, which is also higher than the hypothesized OR = 2.5. Therefore, we are confident that the sample size goal will be sufficiently powered to detect intervention effects on key variables for SA1 and SA2. Finally, the sample size estimate does not reflect our plans to conduct analyses based on repeated measurement of outcome variables at the 1, 2, 3, 6, 9-, 12-, 18-, and 24-week time points (due to the dearth of information regarding 24-week outcomes). Generally, the inclusion of data for an outcome variable across additional time points marginally enhances statistical power, especially for testing "main" and "interaction" effects of intervention and time.

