**SA1.** Initially, mixed effects linear modeling will be applied to contrast mean levels of pain at the 1-, 2-, and 3-week time points. The analyses will be repeated for a series of pain outcome measures, including BNP intensity, BNP interference, and cumulative BNP. The models will include “main” effects for intervention and time, an interaction between intervention and time, a random effect for “subject”, and the baseline value of the dependent variable as a covariate. Modeling results will be used to test for a time-by-intervention interaction. If the interaction is non-significant, the model will be re-fitted without it and testing will focus on the main effect of intervention. Regression diagnostics will be applied to all models to identify non-normality in residuals and potentially biasing effects of outlying observations. While mixed effects linear models are resistant to the impact of limited amounts of missing data, we will also utilize multiple imputation methods, as described below, to evaluate the sensitivity of model estimates and testing results to missing observations. Following evaluation of intervention effects at the 1-, 2-, and 3-week time points, we will proceed to assess differences in acute and cumulative BNP intensity and interference at 6, 9, 12, 18 and 24 weeks. Additionally, we will investigate whether subject-level “trends” or “growth curves” in pain levels across all eight study time points differ between the intervention and control conditions. If necessary, demographic variables will be included in the regression models both to account for potential confounding effects that might arise via imperfect randomization and to reduce unexplained between-subject variation in outcome variables.

**SA2. H2A.** We will start by investigating the intervention's effect on proportion of exclusive BF after week 6. Initially, the Pearson Chi-square test will be performed to detect the difference between intervention and control groups at 6, 9, 12, 18, and 24 weeks, respectively. Furthermore, a generalized linear mixed model with a logistic link will be applied to analyze the “main effect” of intervention and time, and “interaction effect” of intervention by time. The procedure to fit and re-fit the model will be similar to the approach for pain measures in SA1. The measure for BF self-efficacy, yield scale scores

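### SA1's test-then-refit rule for two primary pain outcomes names no deciding contrast, no both-or-either requirement and no alpha control, so its false-positive rate and power depend on a rule that is not written

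*Combined protocol and SAP*

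**What the plan says.** The specific aims (Purpose/Introduction) describe SA1 as concerning "the primary outcome of BNP intensity and interference between the intervention and attention control group". H1 is directional and joins its parts with 'and': the BSM "group will report significantly lower BNP intensity and interference at 1, 2, and 3 weeks and significantly lower cumulative BNP score over time".

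The SA1 paragraph of Data Analysis and Management fits a mixed model with the baseline value as covariate "to contrast mean levels of pain at the 1-, 2-, and 3-week time points". It tests intervention-by-time first. Then: "If the interaction is non-significant, the model will be re-fitted without it and testing will focus on the main effect of intervention". The procedure is not run once: "The analyses will be repeated for a series of pain outcome measures, including BNP intensity, BNP interference, and cumulative BNP". The paragraph gives no significance level, no contrast to follow a significant interaction, no order of outcomes and no definition of success. The SA2 paragraphs carry the same fit-and-refit approach to exclusive breastfeeding, breastfeeding self-efficacy and well-being.

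For comparisons between the arms, the 0.05 level appears only in Justification of Sample Size, attached to one comparison: "two-sided) to detect a standardized mean difference" of 0.39. That section adds that "the sample size estimate does not reflect our plans to conduct analyses based on repeated measurement of outcome variables". It also reports that the pilot d for interference "was 0.39 at week 1, but smaller at weeks 2 and 6". False-positive control is described only for the methylation sequencing and array analyses.

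**The concern.** The test to be reported is chosen by the result of another test on the same data. If the interaction is not significant, the refitted main effect is tested. If it is significant, the text stops. Weekly contrasts would be the natural next step, since contrasting the weekly means is the model's stated purpose, but the plan does not say so or say which week decides.

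The procedure is applied to two primary outcomes, and H1 is never linked to it. The same data could therefore make SA1 positive or negative, depending on a reading adopted after the results are seen. Some readings inflate the false-positive rate. Others do not, but can leave power well below the 80% quoted for the trial.

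**Working it through.** **Reproducing the plan's figure.** For one two-group comparison at two-sided 0.05, 80% power and d = 0.39: n per arm = 2 × (1.96 + 0.842)² / 0.39² = 103.2, so 104. Then 208 / 0.75 = 277.3, so 278 against the stated 280. With 25% loss, 140 × 0.75 = 105 per arm gives 80.3% power. The figure is right, but for a single comparison.

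**Assumptions the documents do not supply.** Interaction tested at 0.05; correlation between visits 0.3–0.7; correlation between the two outcomes 0–0.9; complete data; equal correlation between visits.

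**False positives by formula (any significant test counts).** Under equal visit correlation the interaction and main-effect tests are independent.
- One outcome: 1 − 0.95² = 9.75%.
- Two uncorrelated outcomes, either: 1 − 0.95⁴ = 18.5%.
- Both: 0.0975² = 0.95%.
- In general, either = 2 × 9.75% − both. At outcome correlation 0.9, both is about 5.9%, so either is 19.5 − 5.9 = 13.6%.

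**False positives by simulation.** 105, 132 or 140 per arm, except that the favouring-BSM 'both' figures were run at 105. The interaction is a 2-df F test. The main effect is a baseline-adjusted comparison of the weeks 1–3 mean, and the weekly contrasts are also baseline-adjusted.

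| Reading | Per outcome | Either outcome | Both outcomes |
|---|---|---|---|
| Any significant test counts | 8.8–10.5% | 12.6–19.4% | 0.8–6.1% |
| Significant interaction also needs a significant weekly contrast | 6.5–8.4% | 9.7–15.9% | 0.5–4.8% |
| As the row above, only results favouring BSM count (nominal 2.5%) | 3.1–4.2% | 4.8–8.1% | about 0–2.5% |
| Significantly lower at every week, on both outcomes | – | – | at most 0.05% |

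**How often the branch without a stated follow-up is reached for interference.** The interaction test has noncentrality λ = (n/2) × Σ(d_t − d̄)² / (1 − ρ), where ρ is the visit correlation. For d = 0.39/0.20/0.20: d̄ = 0.2633 and Σ = 0.02407. With n = 105 and ρ = 0.3, λ = 52.5 × 0.02407 / 0.7 = 1.805, giving 20.6%.

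For the averaged contrast, the residual variance given baseline is v = (1 + 2ρ)/3 − ρ², and the noncentrality is d̄ / √(2v/n). For 0.39/0.20/0 with n = 105 and ρ = 0.3: v = 0.4433 and 0.1967 / 0.0919 = 2.14, giving 56.8%. With n = 132 (6% pilot attrition) and ρ = 0.7: v = 0.31 and 0.1967 / 0.0685 = 2.87, giving 81.6%.

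Ranges over 105 and 132 per arm and ρ = 0.3–0.7, with d in single-visit SD units:

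| Assumed d, weeks 1/2/3 | Interaction significant | Averaged contrast significant |
|---|---|---|
| 0.39/0.35/0.35 | 5.6–6.8% | 97.6% or more |
| 0.39/0.30/0.30 | 8–15% | 94.7–99.8% |
| 0.39/0.20/0.20 | 20.6–52.6% | 81.4–96.9% |
| 0.39/0.20/0.10 | 34.4–79.4% | 70.2–91.7% |
| 0.39/0.20/0 | 55.8–96.3% | 56.8–81.6% |

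Under 0.39/0.20/0.10, interference is significant at all three weeks in only 5.4–16.7% of trials.

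**The case against.** The strongest reply is that H1 already supplies the rule. It is directional and joins intensity and interference with 'and', so both must succeed in favour of BSM, and there is then no inflation and no alpha to share. On the arithmetic this stands: 0–2.5%, and close to zero if every week must be significant. A reader might infer from the first row of the table that SA1 runs at 13–19%. The documents do not support that as the trial's error rate. It needs either outcome to suffice, any significant interaction to count whatever its shape, and results favouring control to count as well. No section says these things, and H1 points the other way.

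H1 is nevertheless a hypothesis, and the analysis section never turns it into a decision rule. Read literally, it requires significance at each of three weeks on both outcomes, plus cumulative BNP. A refitted main effect gives one estimate across weeks and does not test that.

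A reader might also infer from the pilot that a significant interaction for interference is likely. The plan says only that the effect was smaller at weeks 2 and 6. It gives no values for those weeks, and the pilot had no week 3 assessment. Mild to strong assumed fades give anything from about 6% to 96%, so the branch is possible but its probability cannot be fixed.

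It is also fair to say that test-then-refit is a common modelling sequence, and that averaging over weeks is one choice among several. That bears on which contrast to choose, not on whether to name one.

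The choice of intensity instrument (VAS or Brief Pain Inventory) and the two statements on blinding of the analysis are separate points, and this one does not rest on them.

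**Conclusion.** The concern holds as a gap in the decision rule. Taken outcome by outcome, the two-step rule exceeds 5% two-sided: about 6.5–8.5% with a required weekly contrast, and about 9–10% if any test counts. Across the two outcomes the rate depends on the unwritten rule: 10–16% (weekly contrast required) or at most 13–19% (any test) if either may succeed; 5–8% against a nominal 2.5% if either may succeed and only results favouring BSM count; and 0–2.5%, with no inflation, if both must favour BSM.

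The last reading is closest to H1. Its literal week-by-week form, however, is not what the refitted model tests, and under a fading interference effect its power can fall far below the 80% quoted for a single comparison.

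All the rates rest on the assumed correlations and a 0.05 interaction test. The power figures also rest on assumed effects at weeks 2 and 3. This should be fixed; it does not show that SA1 will produce a false result.

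**What to change.** Drop the test-then-refit step and keep intervention-by-time in the model. For each primary outcome prespecify one confirmatory baseline-adjusted contrast, for example the between-arm difference averaged over weeks 1–3, and report the weekly contrasts alongside. State whether H1 needs both outcomes, in which case no alpha split is needed, or either, in which case test them in a fixed order at two-sided 0.05. With that order the error rate across the two is 5%. With one contrast per outcome but no order it would be 6–10%. Treat cumulative BNP and weeks 6–24 as supportive.

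State that 80% power at d = 0.39 is for one comparison, and recompute power for the chosen rule, including a fading interference effect. Use the same wording where SA2 borrows the procedure. Date the amendment before any further by-arm analysis. Record any interim look already made, since the study timeline provides for an interim analysis article and the monitoring board reviews preliminary data every three months.

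The cost is SAP wording and a few lines of code, with no new data. There are real downsides. H1's weekly and cumulative claims become supportive, which changes the hypothesis as worded. Under a fixed order the second outcome cannot be claimed if the first fails. If the interference effect fades to zero by week 3 (assumed 0.39/0.20/0), the averaged contrast has about 57–82% power. If d = 0.39 holds at every week, both averaged contrasts succeed in 97.7–99.9% of trials at 105 per arm.

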### **Enrollment and Randomization**

After informed consent and prior to the start of data collection, the participants will be randomized to the *BSM* intervention or the attention control group and be assigned a unique participant identification number (PID#). The sample size objective for the study is to recruit N = 280 women who will be randomly assigned to the *BSM* or attention control study groups at a 1:1 ratio (140 per group). Random assignment will be performed using an established dynamic minimization algorithm, proposed by Pocock and Simon. The algorithm is implemented thru an R package called "minirand", developed by Jin et al.. The interactive tool is developed as an R shiny app embedded in REDCap. This technique will maintain the 1:1 ratio between participants assigned to the *BSM* and control conditions, but will also ensure that participant characteristics that are known to be predictive of breastfeeding outcomes will each be balanced across the study groups. Those predictive characteristics include: age, race, breastfeeding experience, expected breastfeeding duration, route of delivery, and intent to return to work.

The reason we choose this algorithm is the complexity of the randomization needed for our study. With 280 expected participants and 6 stratifying characteristics, the simple randomization may not yield a balanced arm assignment in every allocation. However, the dynamic feature of our randomization will incorporate both the existing assignments and the imbalance at each level of the stratifying characteristics and assign the next participant to minimize the overall imbalance. With the large number of total enrollments in our study, this also leads to a balanced assignment at each level of the stratifying characteristics. To retain randomness, the probability of making the "best assignment" to minimize imbalance is set to be 90%.

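### Exclusive breastfeeding is first tested by five unadjusted chi-square tests although allocation is minimised on six prognostic factors, and no analysis is named as deciding H2A

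*Combined protocol and SAP*

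**What the plan says.** All places are in the combined protocol and SAP.

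- **Data Analysis and Management, SA2, H2A.** The first analysis of exclusive breastfeeding is a comparison at each of weeks 6, 9, 12, 18 and 24: "Initially, the Pearson Chi-square test will be performed to detect the difference between intervention and control groups". After that, "a generalized linear mixed model with a logistic link will be applied", with intervention, time and their interaction. Fitting and re-fitting follow the SA1 approach. Under SA1, the interaction is dropped if non-significant, and demographic variables enter only if needed, with no list.
- **Enrollment and Randomization.** Minimisation, with a 90% probability of the best assignment, is used so that "participant characteristics that are known to be predictive of breastfeeding outcomes will each be balanced across the study groups". The factors are age, race, breastfeeding experience, expected breastfeeding duration, route of delivery and intent to return to work.
- **Justification of Sample Size.** For this outcome: "It also provides 80% power to detect an odds ratio of 2.5 or more in exclusive BF between the two groups". The calculations allow for 25% loss at 24 weeks. The control rate is tied to a national rate that is not stated.
- **Purpose/Introduction.** Exclusivity is a secondary outcome under SA2. H2A predicts a higher proportion at all five weeks and gives no rule for combining them.

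Error control is stated only for the methylation and EPIC array analyses.

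**The concern.** The design spends effort on balancing six factors, and the first analysis then discards that information. When a prognostic factor is balanced by design, the true variance of the difference in proportions is smaller than the variance the Pearson test assumes. The test then rejects too rarely under the null and loses power.

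The logistic model could recover this, but the plan does not commit it to the six factors. Four of them (breastfeeding experience, expected duration, route of delivery and intent to return to work) are not plainly demographic. Adjustment for prior breastfeeding experience is written for SA1 only.

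Nor does the plan rank the analyses. Five weekly p-values, an interaction test and a possible main-effect test could all bear on H2A. If they disagree, the choice of headline result would be made after the data are seen.

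**Working it through.** **1. The plan's own sample size.** Inputs from Justification of Sample Size: d = 0.39, two-sided 0.05, 80% power, 25% loss.
n per arm = 2 × (1.960 + 0.842)² / 0.39² = 15.70 / 0.152, which rounds up to 104.
104 / 0.75 rounds up to 139 per arm, so N = 278 against 280 stated. The figure reproduces.
Retained at 24 weeks: 140 × 0.75 = 105 per arm.

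**2. The exclusive breastfeeding statement.** Unadjusted comparison of two proportions, odds ratio 2.5, 105 per arm. The control rate p₀ is not given, so a range is shown.
Example at p₀ = 0.40: odds 0.667 × 2.5 = 1.667, so p₁ = 0.625. The null SE is √(2 × 0.5125 × 0.4875 / 105) = 0.0690 and the alternative SE is √((0.240 + 0.234) / 105) = 0.0672. Power = Φ((0.225 − 1.96 × 0.0690) / 0.0672) = Φ(1.34) = 0.909.

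| Control rate | 0.10 | 0.15 | 0.20 | 0.40 | 0.65 | 0.70 | 0.80 |
|---|---|---|---|---|---|---|---|
| Power | 0.645 | 0.773 | 0.842 | 0.909 | 0.816 | 0.766 | 0.612 |

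The 80% claim holds for control rates of about 0.17 to 0.67.

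**3. Cost of ignoring the factors.** Simulated minimisation with N = 280, best-assignment probability 0.90, 25% loss at random and 4,000 trials per cell. Assumed: six binary factors with prevalence 0.5, each with the same odds ratio. The intervention odds ratio is 2.5 conditional on the factors. Comparison: chi-square versus logistic regression on intervention plus the six factors.

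| Each factor's OR | Null rejection, chi-square | Null rejection, adjusted | Power, chi-square | Power, adjusted | Gain |
|---|---|---|---|---|---|
| 1.0 | 4.9% | 5.4% | 91.0% | 90.9% | about 0 |
| 1.5 | 4.9% | 5.7% | 87.1% | 88.6% | about 2 |
| 2.0 | 4.0% | 5.9% | 83.0% | 87.3% | about 4 |
| 2.5 | 3.0% | 5.0% | 75.5% | 83.6% | about 8 |

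The Monte Carlo standard error of a null rate is about 0.35 points. The gain column is the result. The absolute chi-square powers are not a test of the plan's 80%, as step 4 shows.

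**4. Conditional and between-group odds ratios differ.** Take one balanced factor with log-odds ±1.1, that is exp(2.2) ≈ 9 between levels, and a conditional odds ratio of 2.5 (log 0.916). With a control rate of 0.50, the intervention rate is the mean of expit(2.016) = 0.883 and expit(−0.184) = 0.454, which is 0.668. The between-group odds ratio is then 0.668 / 0.332 ≈ 2.0. In this setting chi-square power is about 71–73% and null rejection 2–3%. If instead the between-group odds ratio is set at 2.5, with the same factor and control rates of 0.32–0.50, chi-square power is about 93%.

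**5. Five weekly tests.** If independent, 1 − 0.95⁵ = 0.226. Exclusive breastfeeding status is correlated across weeks, so correlated normal statistics were simulated. Ranges cover equal and autoregressive correlation.

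| Correlation (assumed) | Each test rejects 5% | Each test rejects 2.5% |
|---|---|---|
| 0.9 | 10–12% | 5–6% |
| 0.5 | 18–20% | 10–11% |

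These are chances of at least one false positive if success at any single week counted.

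**The case against.** Four points can be made for the plan.

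- **The logistic model already follows.** It can give one main-effect test, and the SA1 covariate rule exists partly to reduce unexplained variation; age and race would plausibly enter. This stands in part. The model is the right vehicle, but its covariates are conditional and unlisted, and it is not named as decisive.
- **The power loss depends on factor strength.** The documents give no factor effects. With weak factors the loss is 2 points or less. This stands, and the size must be given as a range.
- **The sample size is not undermined.** A reader might infer from chi-square powers in the seventies that the 80% claim fails. It does not follow. Justification of Sample Size states an odds ratio between the groups against a control-group rate, whereas those powers belong to a smaller between-group effect of about 2.0. At 2.5 between groups, under the same strong factor, the chi-square test is at about 93%.
- **H2A claims no any-week success.** If all five weeks were required, there would be no inflation. A reader might also set a 2.5% per-test rejection rate beside a 10–20% family error and count both. They cannot hold together, because the 10–20% assumes that each test rejects 5%.

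**Conclusion.** The point holds as a gap in the analysis specification for a secondary outcome. The first-listed tests ignore the minimisation factors, the follow-on model does not commit to them, and no analysis is named as deciding H2A.

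The power forgone is about 2, 4 or 8 points for factor odds ratios of 1.5, 2.0 or 2.5, under equal binary factors, loss at random and a conditional intervention odds ratio of 2.5. The documents do not support a claim that 80% power is missed. That claim cannot be confirmed at every week either, because the control rate is not stated.

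Multiplicity is a secondary point. It matters only if success at any one week is claimed, a rule the plan neither states nor excludes, and the conservatism of the chi-square tests partly offsets it.

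**What to change.** In the H2A text:

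1. Name the planned logistic repeated-measures model as the analysis that decides H2A for exclusive breastfeeding.
2. List the six minimisation factors as prespecified covariates, replacing the conditional rule for this outcome.
3. Fix one contrast, the average intervention effect over weeks 6–24, tested once at two-sided 0.05 whatever the interaction test shows.
4. Report weekly odds ratios with confidence intervals as estimates. Any chi-square tests that are kept should be labelled descriptive.
5. Also report the group proportions or a standardised (marginal) odds ratio. The adjusted odds ratio is conditional and does not correspond to the between-group odds ratio in Justification of Sample Size.

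The cost is SAP wording: the six factors are already entered at randomisation, and no participants are added. The downside is that no stand-alone weekly significance claim can be made. Adjustment also needs some care, since the simulated adjusted test rejected up to 5.9% under the null. The alternative, Bonferroni at 0.01 per week, would cut weekly power at a between-group odds ratio of 2.5 to about 55–76% for control rates of 0.15–0.65; a single contrast avoids that split.

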### **IFSMT Distal Outcomes.**

#### **Health Status.**

**Exclusivity and Duration of BF** measured by the Ongoing BF Assessment Survey and the BF algorithm.

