which range from 14-70. We will treat BF self-efficacy scores as "continuous" variable and follow the approach in SA1 to investigate the intervention effect on BF self-efficacy over time. **H2B.** Subsequently, we will assess intervention effects on maternal well-being - anxiety, depressive symptoms, fatigue, stress, and sleep disturbance over all the time points. Each of these variables' measurement scores will be treated as "continuous" and effects of the *BSM* intervention will be investigated following a similar approach as for the pain measures in SA1. Because these variables are highly interrelated, we will evaluate their response to intervention effects simultaneously. In this approach, differences in the quadrivariate means of these variables between the *BSM* and attention groups will be analyzed using multivariate mixed effects linear modeling in an approach analogous to that for the pain measures in SA1 but with the inclusion of covariances between random intercepts for the anxiety, depressive symptom, fatigue, and sleep disturbance scores at the subject level. Across the modeling procedures related to SA2, regression diagnostics will be applied to investigate suitability of distributional assumptions and potential biasing effects of outliers.

**SA3.** We will model effects of pain sensitivity SNPs on quantitative sensory testing measures, BNP intensity and interference, BF outcomes in SA2, and maternal and pain self-efficacy across all the time points. In addition, we will also assess the effects of individual quantitative sensory testing measures on all the outcome measures aforementioned over time. Analyses will utilize "linear/generalized linear" modeling with univariate and multivariate dependent variables, will account for correct temporal ordering among time varying measures, and will evaluate correlations between measures that jointly vary in time in response to other factors/covariates.

We have planned for attrition rates as high as 25%. However, our goal is to minimize attrition by instituting a participant outreach plan –namely, contacting participants to complete modules, providing monthly updates regarding child development, and encouraging women to remain involved. In statistical analyses, we will follow each model based only on "observed data" with sensitivity analyses in which Markov Chain Monte Carlo multiple imputation is used to assess the possibility and impact of "missing at random" data.

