#### **Post Enrollment Exclusion Criteria**

Participants who are enrolled in the study may be withdrawn due to any of the following criteria:

- non-compliance with study procedures such as failing to log daily entries and completing data collection points. At each data collection point, participants will be reminded via text to complete the surveys, with pushes from REDCap as needed to encourage completion. If needed, participants are followed up with a phone call or email to complete the surveys. If they do not complete the survey, they will be contacted for the next data point. If they do not complete three consecutive data points, they will be removed from the study, however any data collected will be used in analysis.
- Participants will be removed from the study at their own request.

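### H2A has no rule for a woman who reports stopping breastfeeding and then misses visits, so reported exclusivity is overstated if such women respond less

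*Combined protocol and SAP*

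**What the plan says.** Under Data Analysis and Management, SA2 (H2A), the first step for exclusivity is that "the Pearson Chi-square test will be performed to detect the difference between intervention and control groups at 6, 9, 12, 18, and 24 weeks". A generalized linear mixed model with a logistic link follows. The attrition paragraph after SA3 says "In statistical analyses, we will follow each model based only on" observed data, then adds sensitivity analyses by Markov chain Monte Carlo multiple imputation under missing at random.

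The outcome is defined in the Significance section as breast milk only, without a time window. IFSMT Distal Outcomes, Health Status, says exclusivity and duration are "measured by the Ongoing BF Assessment Survey and the BF algorithm"; Table 2 schedules both instruments at all nine time points.

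Post Enrollment Exclusion Criteria removes a woman after three consecutive missed data points, "however any data collected will be used in analysis".

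No section says how exclusivity is derived at a missed visit when an earlier survey reported that breastfeeding had stopped.

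**The concern.** Take a woman who reports at week 3 that she has stopped completely and then misses weeks 6, 9 and 12. She is removed and has no record at weeks 18 or 24. The plan keeps her week 3 report but gives H2A no means of using it later. A Pearson test cannot include a missing value, so she leaves the denominator at every one of the five visits. Imputation could give her a value that contradicts her own report.

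This is not a general complaint about the missing-at-random assumption. After complete cessation the later binary status follows from recorded data unless she resumes. Because weaned women may have less reason to keep answering, the loss may depend on the outcome itself. At stake are the reported proportions, which the pilot-results section expects to exceed national rates, and the five visit-specific tests.

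**Working it through.** **The plan's own figures.** Justification of Sample Size states: "This objective provides 80% power" for a standardized difference of 0.39, two-sided 5%, with up to 25% loss. Check: n = 2 × (1.960 + 0.842)² / 0.39² = 103.2, so 104 per arm; 104 / 0.75 = 138.7, so 139 per arm, 278 in total against 280 stated. This reproduces. The same section claims "80% power to detect an odds ratio of 2.5 or more in exclusive BF between the two groups". That cannot be checked exactly, because the control rates are not given. At 105 per arm (140 × 0.75), power is at least 80% for control rates of about 0.20 to 0.65.

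**Assumed inputs.** The documents give no rates for this problem. I assume at week 24, identically in both arms: 35% exclusive, 25% partial, 40% weaned. Women still breastfeeding respond with probability 0.90, weaned women with probability r.

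**Observed exclusivity** = 0.35 × 0.90 / (0.35 × 0.90 + 0.25 × 0.90 + 0.40 × r) = 0.315 / (0.540 + 0.40r)

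| r | Denominator | Observed (true 35%) |
|---|---|---|
| 0.70 | 0.820 | 38.4% |
| 0.60 | 0.780 | 40.4% |
| 0.50 | 0.740 | 42.6% |
| 0.40 | 0.700 | 45.0% |

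**Equal silence.** Both arms are inflated alike. With no true effect the odds ratio is 1 and the test rejects 5% of the time.

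**Unequal silence, no true effect, 140 randomized per arm.**
- 50% (BSM) v 70% (control): OR = (0.426/0.574) / (0.384/0.616) = 1.19. Observed n = 140 × 0.74 = 103.6 and 140 × 0.82 = 114.8. Pooled standard error 0.0665; difference 0.0416; z = 0.626. Rejection = Φ(0.626 − 1.96) + Φ(−0.626 − 1.96) = 9.6%.
- 40% v 70%: OR = 1.31; n = 98 and 114.8; rejection 16.3%.
- Arms reversed in the first case: OR = 1/1.19 = 0.84, which would hide a benefit.

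Average loss is (26% + 18%)/2 = 22% in the first case and (30% + 18%)/2 = 24% in the second, although 30% in one arm exceeds the planned maximum.

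**Range at the plan's 25% loss in each arm.** Observed = [p − (1 − f)mp] / (1 − m), where p is the true rate, m the share missing and f the share of the missing already known to have stopped. For p = 0.30, 0.35 and 0.50, observed is 0.40, 0.467 and 0.667 if f = 1, and 0.35, 0.408 and 0.583 if f = 0.5.

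**Mixed model.** I simulated 140 per arm with no true effect. True exclusivity fell from 55% to 35% over the five visits, and women could go silent after losing exclusivity. With 12% v 36% missing at week 24, the week 24 chi-square rejected in 56% of runs. The mixed model's intervention effect rejected in 9.4%, against 7.8% when silence was equal (24% in each arm). With about 800 runs each, that gap of 1.6 points has a standard error of about 1.4 points.

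**With known stoppers counted as non-exclusive.** If every weaning was reported, the rate is 0.315 / (0.315 + 0.225 + 0.40) = 33.5% in both arms, OR 1.0. If only half of the silent weaned women had reported it, the ORs of 1.19 and 1.31 fall to 1.08 and 1.12. The 33.5% lies below 35% because women still breastfeeding who do not respond remain missing. If their response were 95% v 80%, the rates would be 0.3325/0.97 = 34.3% and 0.28/0.88 = 31.8%, OR 1.12 with no true effect.

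**The case against.** The strongest reply is that the plan is silent rather than wrong. It keeps data already collected, a reported stop is such data, and the observed-data wording attaches to each model rather than to the derivation of the endpoint. So exclusion is an inference. That is fair, but no other rule is given, and a complete-case chi-square is what an analyst following the text would run.

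A reader might go further and infer that the trial is likely to show a false benefit, because only BSM women have daily logs and breastfeeding coaching, and failure to log is a listed ground for withdrawal. The documents do not support that. Table 1 ends logs and coaching near day 40. From week 9 both arms have the same surveys, infant-development modules and payments with a completion bonus. The surveys also cover mood, sleep, fatigue and parenting confidence, so a weaned woman still has something to answer. Every response rate above is assumed, and the pilot lost only 6%, though over 6 weeks.

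It also stands that the mixed model retains her earlier visits and removes most of the false difference, that imputation is only a sensitivity analysis, and that the proposed rule is neither complete nor free of bias. None of this removes the inflation of the reported proportions.

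**Conclusion.** The point holds in a limited form. Under H2A as written, women with a reported complete stop leave the visit-specific chi-square tests and proportions once they fall silent. If weaned women respond less than others, exclusivity is overstated in both arms, by about 5 percentage points in the example (40.4% v 35%), and by more if most of a 25% loss consists of known stoppers. This rests on assumed response rates and on treating a complete stop as lasting unless resumption is reported.

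A distorted arm difference additionally needs silence that differs by arm. That is possible but not shown, and it could favour either arm; OR 1.19 with about 10% type I error is an illustration, not a forecast. The logistic mixed model is much less affected. Exclusivity is a secondary outcome, so it would be wrong to infer that the primary pain analysis or its sample size is compromised.

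**What to change.** Add a derivation rule to H2A: a woman whose latest completed survey reports complete cessation, with no later report of resuming, counts as non-exclusive at later missed visits, including after removal. Apply it before the chi-square tests, the mixed model and the imputation.

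Leave women last seen exclusively or partly breastfeeding as missing, and impute them with last feeding status in the imputation model, since counting only known stoppers slightly understates exclusivity. Report missingness by arm and last feeding status, and show the observed-only result as a sensitivity analysis. Fix the rule before any unblinded analysis.

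The cost is a short addition to the analysis text. It needs only the feeding status reported in completed surveys; the sponsor should confirm that the Ongoing BF Assessment Survey separates a complete stop from partial breastfeeding, because the instrument is not reproduced in the documents. Downsides: rare unreported resumption is misclassified, women who stop and go silent between surveys are not recovered, and a small downward bias remains in the unimputed chi-square.
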